6.3 Study procedures

Patients that are diagnosed by the GP with acute sciatica (3-8 weeks after onset of pain, NRS \geq 6) that meet in- and exclusion criteria will be offered the study. If patients are willing to be randomized, they will be contacted by the study investigator. The study investigator will inform the patients again and checks whether patients have access to e-mail. This is done to make sure that they can fill in the questionnaires online (a web-based database with questionnaires is used for data collection (Castor, LUMC)). The study investigator will ask for informed consent. Randomization will take place. If patients are randomized to the intervention group, they will be sent to the anaesthesiologist and planned for TEI within 4 days after randomization without visiting the neurologist. If patients are randomized to the

control group, they will receive oral pain medication according to the care of the general practitioner.

The patient will be invited to the hospital where baseline data will be gathered and questionnaires will be filled in. During this contact the study investigator will guide the patient through the online questionnaire fill-in procedure to get the patient accustomed with this procedure.

Questionnaires will be filled in after 1, 2, 4, 10 and 21 weeks after randomization for both the control group and TEI group.

If leg pain remains severe after the 2 weeks after randomization primary endpoint, patients can be referred to the neurologist if the general practitioner deems it necessary. Patients can be offered surgery if applicable.

If an MRI is made during the process, MRI data will be gathered as mentioned above.

If a lumbar discectomy is performed, disc tissue will be gathered during surgery and analysed as mentioned above.

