3. STUDY DESIGN

This is a prospective, open-label, randomized controlled trial on patients suffering from acute sciatica (3-8 weeks pain in the leg with a NRS ≥ 6) (see inclusion and exclusion criteria) in which consecutive patients who meet the inclusion criteria are invited to participate in the trial. The trial will take place at the Spaarne Gasthuis Hospital (SG) in Hoofddorp and Haarlem, the Netherlands in cooperation with researchers from Leiden University Medical Center (LUMC), Leiden, the Netherlands. Patient recruitment will occur at GP practices (GP collective Haarlemmermeer and Kennemerland, 185 GP's). The GP will diagnose the patient and, if the patient is diagnosed with sciatica, refer to the study investigator.

Eligible patients that are willing to participate are randomized to treatment with transforaminal epidural injections (treatment group) or standard conservative care (control group).

Randomization will take place using block randomization in a 1:1 allocation ratio. Patients from the treatment group will be treated with TEI, oral pain medication and, if deemed necessary by the GP, physiotherapy. The control group will only receive oral pain medication and if deemed necessary additional physiotherapy. For this study, the control group will not include placebo injections since we want to compare treatment with injections to treatment without injections. The focus will not be on the type of medication that is contained in the injection. Furthermore, a control group without injections will demonstrate what percentage of patients will experience spontaneous relief of symptoms (only using medication and/or physiotherapy) as it is known that in a significant part of the patients sciatica resolves without any intervention.

At baseline, clinical and demographic data are gathered for patients in both groups. Patients from the treatment group will receive TEI within 4 days after randomization. Patients from this group can receive multiple injections but an injection is only repeated after a certain interval time according to usual anaesthesiological guidelines. For all injections, details on timing, frequency and prevailing complications will be gathered.

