6.2 Randomisation, blinding and treatment allocation

Randomisation will take place using block randomisation in a 1:1 allocation ratio in order to obtain equal study groups. When the patient is enrolled, a randomization envelope will be opened to determine patient allocation. Since this is an open-label randomized controlled trial allocation is not concealed.

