8.2 Secondary study parameter(s)

The absolute decline in NRS leg pain, NRS back pain and ODI and increase in EQ5D from baseline to 2 weeks after randomization will be calculated using t-tests. The same will be done for the baseline to 4 weeks after randomization time point (using t-tests).

Perceived recovery Likert data will be dichotomized (1 and 2 is success, 3-7 is no success) and compared at 2 and 4 weeks after randomization or injection and to 14 and 26 weeks after start of severe leg pain using Chi-square tests.

The 2-week success data will be correlated to the success data after 14 weeks and subsequently for 26 weeks using Chi-square tests to make predictions. Logistic regression analysis will be used to correlate 2-week (and 4-week) success data to the absolute data for NRS leg pain, NRS back pain, ODI, increase in EQ5D at 14 and 26 weeks.

Cost effectiveness analysis:

The economic evaluation will consist of a cost-effectiveness analysis from a healthcare perspective (CEA: costs per extra patient with symptom relieve, i.e. the primary outcome measure) and a cost-utility analysis from a societal perspective (CUA: costs per QALY). Both analyses will be trial-based, using patient reports, with a half-year time horizon. Healthcare use will be valued according to the Dutch guidelines. QALYs will be calculated as the area under the utility curve, estimated using the Dutch tariff for the EQ-5D. As sensitivity analysis, QALYs will also be calculated using the VAS for quality of life (with power transformation). Average costs and patient outcome will be compared according to intention-to-treat, using net-benefit analysis, and using multiple imputation to account for missing data.

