10. ADMINISTRATIVE ASPECTS, MONITORING AND PUBLICATION

10.1 Handling and storage of data and documents

Data will be collected using Castor EDC (web based secured system provided by LUMC). Baseline data will be collected during inclusion of the participant and directly registered in Castor by a researcher from the LUMC. Data on TEI, MRI and lumbar surgery will be collected from the electronic patient system Epic in Spaarne Gasthuis by the treating physician and by a researcher from the LUMC and processed in Castor. Specific data on the TEI procedure will be filled in on a paper CRF by the anaesthesiologist and subsequently processed by a researcher from the LUMC in Castor. Other data will be collected at predefined follow-up moments through digital questionnaires that the participants will fill in at home. These will be processed automatically in Castor. Castor EDC will code the patient data into untraceable ID's. All data will be safeguarded and stored for 15 years after the study is finished. All data will be handled according to the guidelines of GRP. This obligates all researchers to comply to the quality assurance standards, which include monitoring, risk assessment, privacy of patient data, and transparency of information to the patient. The LUMC will be responsible for the processing of data.

In order to warrant privacy patient data and disc material will be coded. Only with the key data can be traced back to a specific individual. The key is securely saved at the local research site and only the principal investigator, research monitor and Healthcare and Youth Inspection (Inspectie Gezondheidszorg en Jeugd) will have access to the key. No traceable data will be published. Patients will give permission for these authorities to access the key and their personal data through the informed consent. At any moment patients can withdraw their permission. Data collected before withdrawal of consent will be used. If disc material has been collected, it will be destroyed after withdrawal of consent. Analyses of disc material performed before withdrawal of consent will be used.

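### Section 6.3 describes the baseline visit after randomisation and TEI planning, so open-label patients could give baseline scores knowing their arm; the 8.2 change-score tests are exposed, the primary t-test is not

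*Combined protocol and SAP*

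**What the plan says.** Four places bear on when baseline is measured.

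- **Section 6.3 (Study procedures)** runs in sequence: "The study investigator will ask for informed consent. Randomization will take place". TEI patients are then dealt with: "they will be sent to the anaesthesiologist and planned for TEI within 4 days after randomization without visiting the neurologist". Controls go on to oral medication under the GP. A new paragraph follows: "The patient will be invited to the hospital where baseline data will be gathered and questionnaires will be filled in". That visit has no stated time relative to randomisation or injection.
- **Section 6.2** ties allocation to enrolment: "When the patient is enrolled, a randomization envelope will be opened to determine patient allocation". It does not make completed baseline data a condition. It adds: "Since this is an open-label randomized controlled trial allocation is not concealed".
- **Section 3 (Study design)** describes randomisation and the two treatments first, and then says: "At baseline, clinical and demographic data are gathered for patients in both groups".
- **Section 10.1** says: "Baseline data will be collected during inclusion of the participant and directly registered in Castor by a researcher from the LUMC".

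Section 4.1 also passes from signed consent to allocation without mentioning baseline.

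Baseline is used in section 8.2: "The absolute decline in NRS leg pain, NRS back pain and ODI and increase in EQ5D from baseline to 2 weeks" is to be examined with t-tests, and again to 4 weeks. Under 6.1.2 the baseline EQ-5D, and the quality-of-life VAS used in the sensitivity analysis, start the utility curve for the QALYs. The primary analysis in 8.1 compares mean NRS leg pain between arms with an unpaired t-test and names no baseline term.

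**The concern.** A baseline measurement protects a comparison only if it cannot depend on the arm. All the scores concerned are reported by the patient. Someone who has just learned that there will be no injection, or that one is booked in the next few days, may rate pain, disability or health differently for that reason alone. A TEI patient who is injected soon after randomisation and attends the visit later would give a baseline that already contains some treatment effect. Baseline use of pain medication (6.1.3) could likewise be recorded after care has diverged.

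The between-arm comparisons of change in NRS leg pain, NRS back pain, ODI and EQ-5D would then mix treatment effect with arm-dependent reporting. The baseline table would also lose its meaning. Section 1 criticises the earlier acute-phase trial because its control group had better baseline scores. If a similar imbalance appeared here, it could not be told apart from a reporting effect.

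**Working it through.** **1. Order of events, by section**

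| Section | What it fixes | Baseline before the envelope? |
|---|---|---|
| 6.3 | Consent, randomisation, arm-specific care, then baseline visit (narrative order) | Not stated; order suggests after |
| 6.2 | Envelope opened at enrolment | No condition stated |
| 3 | Randomisation described, then baseline | Not stated |
| 10.1 | Baseline during inclusion | Not stated; could be read either way |
| 4.1 | Consent, then allocation | Baseline not mentioned |

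The GP's check of NRS 6 or more (4.1) does precede randomisation. It is nowhere named as the baseline score, and it does not cover ODI, EQ-5D or the VAS.

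**2. The plan's own figure, for context**

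Inputs from 4.4: difference 1.5, SD 2.6, power 90%, significance 5% (taken as two-sided).

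n per arm = 2 × [2.6 × (1.960 + 1.282) / 1.5]² = 63.1, rounded up to 64, as stated. With 10% loss, 128 / 0.9 = 142.2, against 142 stated. This calculation rests on follow-up means (4.0 and 5.5), so the order of baseline and randomisation does not alter it.

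**3. Effect of a baseline shift**

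I read the 8.2 tests as comparing the arms. Change = baseline − follow-up. If one arm's reported baseline moves by d, the difference in change moves by exactly d. A comparison of follow-up scores alone moves by 0. A baseline-adjusted analysis with correlation ρ moves by ρ × d (for example 0.5 × 0.5 = 0.25), so adjustment does not remove the problem.

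The documents give no size for d and no baseline-to-follow-up correlation. Assume SD 2.6 at both times and 64 per arm:

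- SD of change = 2.6 × √(2(1 − ρ)); at ρ = 0.5 this is 2.6.
- SE of the difference = 2.6 × √(2/64) = 0.460.
- With no true effect, rejection probability = Φ(d/SE − 1.96) + Φ(−d/SE − 1.96).
- For d = 0.5: d/SE = 1.088, giving 19.3%.

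Rejection rate of the nominal 5% change-score test with no true effect:

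| Assumed shift d | ρ = 0.3 | ρ = 0.5 | ρ = 0.7 |
|---|---|---|---|
| 0.25 | 7.5% | 8.5% | 10.8% |
| 0.5 | 15.1% | 19.3% | 29.0% |
| 1.0 | 45.2% | 58.5% | 80.2% |

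If the shift works against TEI and the true difference is 1.5, power at ρ = 0.5 and d = 0.5 falls from 90.4% to 58.5%.

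**4. Baseline taken after injection**

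If a fraction f of TEI patients is measured late and their pain has fallen by about 2 points (both assumed), the TEI mean change shrinks by 2f: 0.10 × 2 = 0.2 points and 0.25 × 2 = 0.5 points. This understates the benefit. As a rough plausibility check, section 1 cites 66% responders at about 30 mm and non-responders at 55 mm: 0.66 × 30 + 0.34 × 55 = 38.5 mm, or about 3.9 points. Entry at 6 or more then implies a fall of at least about 2.1. This crosses populations and scales, and it has no control arm.

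**5. QALY curve**

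EQ-5D is measured at 0, 2, 10 and 21 weeks. With linear interpolation (assumed), baseline carries (2 − 0)/2 = 1 week of 21. A between-arm baseline utility shift of 0.05 to 0.10 (assumed) changes QALYs by 0.05/52 to 0.10/52, about 0.001 to 0.002.

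**The case against.** The strongest reply is that the order is inferred from the sequence of paragraphs. Section 6.3 attaches no timing word to the hospital visit. The visit paragraph covers both arms and may simply follow the arm-specific sentences for convenience. Section 10.1 places baseline during inclusion, which fits a single enrolment contact. Figure 1 is where the order would be drawn, and it was not available. All of this stands as far as actual practice is concerned: the documents do not show that any baseline will follow allocation or injection, and a reader who inferred that it definitely will would go too far. It does not remove the gap, because inclusion is also when 6.2 opens the envelope, so 10.1 does not settle which comes first.

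Three other inferences are tempting and are not supported.

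- *The primary result is compromised.* It is not: 8.1 and the sample size in 4.4 use follow-up means only. The 1.5-point difference was set for that comparison and is not a yardstick for bias in the secondary tests.
- *The damage could not be repaired in the analysis.* Change scores with a distorted baseline cannot be corrected reliably, but follow-up scores can be compared directly between the randomised arms.
- *The cost-utility result is seriously biased.* Baseline carries about one week in 21.

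It is also fair to say that the values of d, ρ, f and the early fall in pain are all assumptions.

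**Conclusion.** The concern holds as a gap in the procedures with a limited reach. The text, followed in its written order, permits self-reported baselines from patients who know their arm, and from some TEI patients possibly after the injection; no section that could be checked rules this out. The exposure is confined to the 8.2 change-from-baseline t-tests, the baseline table and, marginally, the QALYs.

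Any bias equals the shift d, and its direction is unknown. Late TEI baselines would understate the benefit, while knowledge of the arm could push either way. At an assumed 0.5-point shift, SD 2.6 and 64 per arm, the false-positive rate of the change-score test is about 19% at correlation 0.5, and 15% to 29% over correlations 0.3 to 0.7. These figures show sensitivity; they do not predict what will happen. The point deserves action because a contaminated baseline cannot be collected again and prevention is a matter of wording.

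**What to change.** Reword 6.2, 6.3 and 10.1, and bring section 3 and Figure 1 into line, so that they state one order:

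1. Informed consent.
2. Hospital visit, with all baseline items (NRS leg and back pain, ODI, EQ-5D, quality-of-life VAS, perceived recovery, pain medication and the other baseline data) completed and time-stamped in Castor.
3. Envelope opened only once the baseline form is saved.
4. Referral for TEI, or return to GP care, as already planned.

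Add to section 8 that any patient whose baseline was recorded after randomisation is listed by arm and kept in the intention-to-treat analysis. As a sensitivity analysis, compare the follow-up scores between arms in all randomised patients without using baseline, at 2 and 4 weeks for NRS leg pain, NRS back pain and ODI, and at 2 weeks only for EQ-5D, which 6.1.2 does not measure at week 4. Do not drop the late-baseline patients: that would select on an event after randomisation which may differ by arm.

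**Cost.** A wording amendment. The visit, questionnaires and database already exist, the sample size is unchanged, and follow-up is already timed from randomisation. The downside is a short wait before randomisation and possibly a few dropouts in that interval; because these precede allocation, they do not bias the comparison.

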6.4 Withdrawal of individual subjects

Subjects can leave the study at any time for any reason if they wish to do so without any consequences. The investigator can decide to withdraw a subject from the study for urgent medical reasons.

6.5 Replacement of individual subjects after withdrawal

This will not be done. Subjects that refuse TEI after randomisation to the TEI group, will be considered as cross-over subjects. Patients that withdraw during the study will be considered lost-to-follow up patients.

6.6 Follow-up of subjects withdrawn from treatment

These subjects will be followed-up according to study protocol and considered as cross-over subjects.

6.7 Premature termination of the study

N.a.

7. SAFETY REPORTING

7.1 Temporary halt for reasons of subject safety

In accordance to section 10, subsection 4, of the WMO, the sponsor will suspend the study if there is sufficient ground that continuation of the study will jeopardise subject health or safety. The sponsor will notify the accredited Medical Ethical Committee (METC) without undue delay of a temporary halt including the reason for such an action. The study will be suspended pending a further positive decision by the accredited METC. The investigator will take care that all subjects are kept informed.

7.2 AEs, SAEs and SUSARs

7.2.1 Adverse events (AEs)

Adverse events are defined as any undesirable experience occurring to a subject during the study, whether or not considered related to TEI. All adverse events reported spontaneously by the subject or observed by the investigator or his staff will be recorded.

Adverse events from treatment with TEI are rare. The most common adverse events reported in literature are [19]:

- Transient exacerbation of pain: 2.4%
- Pain at site of injection: 1.1%
- Persisting numbness: 0.33%
- Vasovagal reaction: 0.14%
- Accidental discal puncture: 0-1%
- Accidental dural puncture: 2.3%
- (Post dura puncture) headache: 0.33-1%

This includes also includes leg pain/inability as a result of TEI that:

- requires hospitalisation or prolongation of existing inpatients' hospitalisation;
- results in significant disability or incapacity;

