NRS leg pain that decreases below the value of 4 (on a 10 point scale) within two weeks after TEI is documented as successful effect of TEI. NRS leg pain that remains higher than a value of 4 at a time interval of two weeks after TEI makes a patient eligible for surgery if the patient requests for surgery. If surgery is requested by the patient (either in the control or intervention group), general guidelines for timing of surgery will be conducted, meaning that the patient is encouraged to postpone surgery till 14-16 weeks after onset of pain. This decision is made using Shared Decision Making and it is possible that the patient is operated before the 14-16 week time point. The patients who are randomized cannot be operated in the first two weeks after randomization, unless sudden loss of strength or a cauda equina syndrome is reported. We expect that during these two weeks TEI will have its effect. Four

weeks after randomization the outcome parameters are measured again to be informed on the late effect of TEI. Patients will be followed up for a total duration of 21 weeks starting from the moment of randomization. Questionnaires will be filled in at baseline, 1, 2, 4, 10 and 21 weeks follow-up. A schematic overview of the study procedures is outlined in figure 1. Note that this figure does not hold into account that it is possible for patients randomized to the treatment group to receive additional injections if necessary.

[figure not shown]

Fig.1 Flow diagram of study procedures

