4. STUDY POPULATION

4.1 Population (base)

Patients suffering from sciatica that visit the general practitioner (GP collective Haarlemmermeer (60 GP) and Kennemerland (125 GP) referring to the Spaarne Gasthuis location Haarlem and location Hoofddorp (adherence 750.000 patients) are evaluated to be candidates for this study. If the general practitioner diagnoses a lumbar radicular syndrome (LRS) (sciatica) with an NRS leg pain of 6 points or more on a 10 points scale, and the duration of pain is longer than 3 weeks and shorter than 8 weeks, the patients are offered to participate in the RCT. If they are willing to consider participating in the RCT, the GP will send the contact details to the study investigator. Patients will be offered at least 48 hours to decide whether they want to be enrolled in the study. The study investigator will contact the patients and explain the study again. If patients are deciding to cooperate, informed consent will be signed. If patients are randomized to continue usual care, the GP will be informed and he/she will conduct conservative treatment as deemed suitable. If the patient is randomized to TEI, the patient is referred to the anaesthesiologist to receive TEI. TEI treatment will be received within 4 days.

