5. TREATMENT OF SUBJECTS

5.1 Investigational product/treatment

Patients are referred to the anaesthesiologist to receive TEI within 4 days after randomization.

For injections below L3, where the space around the nerve root is larger and thus dilution of the injectable is more than in the area around the nerve root in the higher lumbar area (above L3), the dosage of the medication will be higher.

For injections at L3 or below :1,5 ml lidocaine 2% and 40mg methylprednisolone acetate is injected transforaminally in close proximity of the nerve root, according to usual care

For injections above L3: 1,5 ml lidocaine 1% and 10mg dexamethasone is injected transforaminally in close proximity of the nerve root, according to usual care.

Administration of the injection will be performed in an outpatient clinic setting and will take 15 minutes. After the procedure, the patient will stay at the recovery room for 30 minutes for monitoring.

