6. METHODS

6.1 Study parameters/endpoints

6.1.1 Main study parameter/endpoint

NRS leg pain: The pain intensity in the leg and the back will be measured with a 10-point horizontal Numeric Rating Scale (NRS), ranging from 0 (no pain) to 10 (worst imaginable pain). During each visit the NRS leg pain and NRS back pain will be scored. The patient is not entitled to see the pain scores indicated during previous visit(s). The NRS scores will be measured at baseline and at 1, 2, 4, 10 and 21 weeks after randomization.

The average score for NRS leg pain at two weeks after injection is compared to the average score for NRS leg pain in the prolonged conservative care group, 2 weeks after randomization. This will be calculated again at 4 weeks after randomization.

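### Adverse events are captured passively, and no instrument or time point is given for complications after the 30-minute recovery stay, so delayed events may be under-recorded and the arms are observed unequally

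*Combined protocol and SAP*

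**What the plan says.** Section 7.2.1 counts an adverse event "whether or not considered related to TEI", so the definition applies to controls as much as to TEI patients. Its capture rule is: "All adverse events reported spontaneously by the subject or observed by the investigator or his staff will be recorded".

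The contacts through which an event could be reported or observed are these:

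- **Both arms.** Section 6.3 describes one hospital contact, for baseline data, and then: "Questionnaires will be filled in after 1, 2, 4, 10 and 21 weeks after randomization for both the control group and TEI group". Section 10.1 gives the mode: "Other data will be collected at predefined follow-up moments through digital questionnaires that the participants will fill in at home". The follow-up instruments in 6.1.1 and 6.1.2 are NRS leg and back pain, ODI, EQ-5D, quality-of-life VAS, Likert recovery and cost diaries. None is described as asking about adverse events. Sections 6.1.1 and 6.1.2 nevertheless speak of visits: "During each visit the NRS leg pain and NRS back pain will be scored".
- **TEI arm.** Section 5.1: "After the procedure, the patient will stay at the recovery room for 30 minutes for monitoring". Section 3 plans to gather complications for every injection. Section 6.1.2 makes complications a secondary parameter and defines a clinically relevant exacerbation as more than 1 extra point of leg pain for at least 24 hours. Section 6.1.3 lists an NRS leg pain score after injection and other complications among the TEI data. Section 10.1 adds a paper CRF on the procedure and data from the hospital record.
- **Control arm.** Section 4.1: "If patients are randomized to continue usual care, the GP will be informed and he/she will conduct conservative treatment as deemed suitable". No complication field is listed for these patients.

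Sections 8.1 to 8.3 contain no analysis of adverse events or complications, and section 11.2 sets up no DSMB or safety committee.

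**The concern.** The capture rule depends on the patient volunteering an event or on staff seeing it. Once follow-up moves to home questionnaires with no described adverse-event question, no scheduled contact prompts the first, and there is little occasion for the second. Several TEI complications named in the protocol (exacerbation of at least 24 hours, persisting numbness, headache) are largely established after the patient has left recovery.

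Two things are at stake. First, the complication parameter in 6.1.2 may be under-recorded for the delayed events, and its one quantitatively defined component has no described means of measurement. Second, a comparison of adverse events by arm would mix any real difference with a difference in observation: TEI patients have a procedure, a recovery stay, a CRF and dedicated fields, and controls have no equivalent. The primary outcome is not affected.

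**Working it through.** **Arm size.** Section 4.4 gives a difference of 1.5, SD 2.6, power 90% and significance 5% (taken as two-sided, which is not stated). n = 2 × (1.9600 + 1.2816)² × 2.6² / 1.5² = 63.1, so 64 per group, as the plan states. 128 / 0.9 = 142.2, against 142 stated. With 1:1 allocation, 142 / 2 = 71 TEI patients. This point changes none of these figures.

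**Can the 24-hour criterion be established from what is planned?**

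- Recovery stay: 30 minutes, against a criterion of at least 24 hours. No.
- Scheduled NRS: TEI is given within 4 days of randomisation (5.1). The week 1 score therefore falls 7 − 4 = 3 to 7 − 0 = 7 days after injection, and the week 2 score 10 to 14 days after. A single score gives no duration. A rise that has settled leaves no trace, and a high score does not show when the rise began or whether it followed the injection.
- NRS after injection (6.1.3): no time is given.
- Procedure CRF (10.1): completed by the anaesthesiologist about the procedure. No later contact is described.

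**Expected events in 71 TEI patients**, from the rates in 7.2.1. Assumptions: one injection per patient, and literature rates that apply per patient.

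| Event | Rate (%) | Largely established after discharge |
|---|---|---|
| Transient exacerbation | 2.4 | yes |
| Injection-site pain | 1.1 | no |
| Persisting numbness | 0.33 | yes |
| Vasovagal reaction | 0.14 | no |
| Discal puncture | 0–1 | no |
| Dural puncture | 2.3 | no |
| Headache | 0.33–1 | yes |

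- All events: low 2.4 + 1.1 + 0.33 + 0.14 + 0 + 2.3 + 0.33 = 6.60%; high 2.4 + 1.1 + 0.33 + 0.14 + 1 + 2.3 + 1 = 8.27%. Times 71: 4.7 to 5.9 events.
- Largely after discharge: low 2.4 + 0.33 + 0.33 = 3.06%; high 2.4 + 0.33 + 1 = 3.73%. Times 71: 2.2 to 2.6 events.
- Share: 3.06 / 6.60 = 46% at the low ends and 3.73 / 8.27 = 45% at the high ends.

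These are events, not distinct patients, because headache can follow a dural puncture in the same patient.

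**Sensitivity to reporting.** The documents give no reporting fraction s, so the values below are assumptions. The chance that at least one exacerbation is recorded is 1 − (1 − 0.024s)^71: 0.82 at s = 1, 0.58 at s = 0.5, and 0.35 at s = 0.25. With 0.024 × 71 = 1.7 exacerbations expected, losing one or two could leave the record empty.

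**The case against.** The strongest reply is that the protocol does not rest on 7.2.1 alone. Sections 3, 6.1.2 and 6.1.3 say that complications will be gathered, documented and recorded. An exacerbation of 24 hours cannot be seen in a 30-minute stay, so post-discharge capture must be intended. Section 7.3 requires every known event to be followed until it settles or is stable. Both arms complete the same questionnaires on the same schedule, and NRS, Likert recovery and the cost diaries give indirect signals in both. The web forms are not reproduced in the documents, so they may ask more than is described.

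Much of this stands, and it rules out several stronger readings:

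- A reader might infer that TEI complications are captured only by chance, or will be missed. The stated intention to gather them does not support that. What is missing is the instrument and the time point.
- A reader might infer that controls are hardly observed or lie outside the hospital record. They complete every questionnaire, and section 10.1 does not limit MRI and surgery data to one arm. Only the TEI procedure data and complication fields are arm-specific.
- A reader might see a safety gap in the exception to the two-week bar on surgery, "unless sudden loss of strength or a cauda equina syndrome is reported". That is a rule on the timing of surgery, not on event capture, and patients remain under GP care.
- A reader might call the SAE reporting clocks defective because they start at first knowledge. Nothing in the documents contradicts that rule.
- A reader might cite the chance of a dural puncture in this arm. A puncture recognised at the procedure is an observed event, and 7.3 already requires its follow-up.

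None of these replies says who asks the patient after discharge, when, or with what form, and none gives controls an equivalent question.

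**Conclusion.** The point holds in a limited form. As described, adverse-event capture is passive and scheduled follow-up is remote. No listed instrument is said to ask about adverse events, and the complication fields are confined to TEI patients. The 24-hour exacerbation criterion cannot be established from the planned measurements. Delayed complications may therefore be under-recorded, and counts by arm would reflect unequal observation.

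On the protocol's own rates, somewhat under half of the expected TEI events are of the exposed kind. This rests on 71 patients with one injection each; section 3 allows repeat injections, which would raise the counts. It is a count of expected events, not of missed ones: the missed fraction cannot be derived from the documents. The change is cheap and should be made, but it does not bear on the primary comparison or the sample size.

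**What to change.** - In 7.2.1, keep the spontaneous rule and add solicited capture: one identical short checklist in the existing web questionnaires at weeks 1, 2, 4, 10 and 21, in both arms. It should cover the events listed in 6.1.2 and 7.2.1, hospital admission, and an open field for anything else.
- For the TEI arm, add an item at week 1, and at the next questionnaire after any repeat injection, asking whether leg pain rose by more than 1 point for at least 24 hours after the injection. Recall will be weaker where questionnaires are far apart (10 − 4 = 6 weeks and 21 − 10 = 11 weeks between the later ones).
- Have positive answers notify the study investigator.
- In section 8, plan to report events by arm, with solicited and spontaneous events shown separately.
- Reconcile the references to visits in 6.1.1 and 6.1.2 with home completion in 10.1.

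Cost: one short form, a notification and an amendment. No visits are added, and treatment and sample size are unchanged. The downside is that more minor events will be recorded and the existing investigator will have some follow-up calls to make.
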